3.4 Analysis Populations

3.4.1 Safety Analysis Population

The Safety population is comprised of all randomized subjects who receive at least one dose of IP. If subjects received the wrong IP at any time during the study, the IP actually received for the majority of the study will be used as the treatment group for that subject.

3.4.2 Intent-to-Treat Population

The ITT population is defined as all randomized. Subjects will be analyzed according to the treatment assigned at randomization, irrespective of dosing adherence or any deviations in the IP received.

3.4.3 Per-Protocol Population

The Per-Protocol (PP) population is defined as subjects from the ITT population who satisfy prerandomization inclusion/exclusion criteria, receive at least dose of IP and complete at least one ontherapy study visit. Individual subject visits and data points that do not satisfy protocol criteria may be excluded from PP analyses. Evaluability will be determined prior to unmasking of treatment assignments.

4 Statistical Methodology

4.1 Definitions and Conventions

Listings present the subjects individual data, while summary tables present the summary statistics of subjects data.

Summary statistics will be presented for continuous variables, by way of n, mean, standard deviation (SD), median, minimum and maximum. For categorical variables including binary variables, frequency counts and percentages will be presented. Percentages will be calculated using the total number of subjects per treatment groups or the total number of subjects with an assessment per treatment groups, depending on the nature of the analysis.

In addition, 95% 2-sided confidence intervals (CIs) will be presented, where relevant. In case of percentages, the CI will be computed using the Clopper-Pearson method. The CI will be computed for continuous variables using a t-test analysis.

Summary statistics will be displayed by treatment groups, which will be labelled as follow:

- Group 1: H-1337 0.6%
- Group 2: H-1337 1.0% b.i.d
- Group 3: H-1337 1.0% q.a.m
- Group 4: Timolol 0.5%

Baseline Value is defined as the last non-missing value prior to the first IP administration for vital signs, BCVA, biomicroscopy and dilated ophthalmoscopy (Day 1 Pre- T_0 for vital signs, BCVA and biomicroscopy; Screening for dilated ophthalmoscopy). For IOP and conjunctival hyperemia grading, time-matched baseline values are defined at Pre- T_0 on Day 1 (Visit 3), T_0 +2 hours, T_0 +4 hours, T_0 +8 hours and T_0 +12 hours on Day 0 (Visit 2). For mean diurnal IOP, baseline is defined at Day 0.

Change from Baseline is defined as the difference in value of the assessment between the considered visit and the baseline value. In the case of IOP and conjunctival hyperemia grading, change from Baseline is the difference in value of the assessment between the considered visit at a particular timepoint and the corresponding baseline value.

Study eye is defined as the eye that meets all entry criteria including the IOP criteria after washout. Should both eyes meet the criteria then the study eye will be the eye with the higher 8 am IOP at Baseline (Day 1). If both eyes have the same 8 am IOP at Baseline (Day 1), the study eye will be the right eye.

SAS® version 9.4 or above will be used to perform the analyses.

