5.1.1 Screening

- Informed consent
- Medical/ocular and concomitant medication history, with review of inclusion/exclusion criteria
 - Any unfavorable medical occurrence should be reported as medical or ocular history
- BCVA
- Biomicroscopy
- Goldmann tonometry
- Gonioscopy
- Pachymetry
- Dilated ophthalmoscopy
- At any time during the visit after informed consent:
 - Urine pregnancy test (if applicable); result must be negative
 - Visual field testing

5.1.2 Day 0

- Medical/ocular and concomitant medication history, with review of inclusion/exclusion criteria
- Urine pregnancy test (if applicable, at any time during the visit); result must be negative
- Any unfavorable medical occurrence should be reported as medical or ocular history
- Heart rate/blood pressure at all required timepoints
- BCVA (may be performed prior to heart rate/blood pressure)
- Biomicroscopy
- Conjunctival hyperemia grading at all required timepoints
- Goldmann tonometry at all required timepoints

5.1.3 Day 1

- Medical/ocular and concomitant medication history, with review of inclusion/exclusion criteria (and again after Pre-T₀ Goldmann tonometry)
- Any pre-dose unfavorable medical occurrence should be reported as medical or ocular history
- Heart rate/blood pressure at all required timepoints
- BCVA(may be performed prior to heart rate/blood pressure)
- Biomicroscopy at all required timepoints
- Conjunctival hyperemia grading at all required timepoints
- Goldmann tonometry at all required timepoints
- Randomization and IP administration immediately after 8 AM T₀ IOP timepoint
- Any post-dose unfavorable medical occurrence should be reported as an Adverse Event

5.1.4 Days 7 and 14

Concomitant medications

- Adverse events
- IP compliance
- BCVA(may be performed prior to heart rate/blood pressure)
- Biomicroscopy at all required timepoints (i.e., Pre-T₀)
- Conjunctival hyperemia grading at all required timepoints (i.e., Pre-T₀)
- Goldmann tonometry (Pre-T₀)
- IP administration (8 AM only)

5.1.5 Day 28

- Concomitant medications
- Adverse events
- IP compliance
- Heart rate/blood pressure at all required timepoints
- BCVA(may be performed prior to heart rate/blood pressure)
- Biomicroscopy at all required timepoints
- Conjunctival hyperemia grading at all required timepoints
- Goldmann tonometry at all required timepoints
- IP administration (8 AM only)
- Urine pregnancy test (if applicable) at any time during the visit

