2.6 Safety Endpoints

The safety endpoints of the study are as follows:

- Incidence of Ocular and systemic Adverse Events (AE),
- The observed blood pressure and pulse, and change from Baseline at each visit,
- The observed best-corrected visual acuity (BCVA) and change from Baseline at each visit.

3 Study Design and Procedures

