4.12.2 Vital Signs

Heart rate and blood pressure (systolic and diastolic), and change from baseline, will be summarized by treatment group, visit and timepoint.

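### Post-dose heart rate and blood pressure changes use the 8 am Day 1 value although Day 0 values at the same hours are collected, so within-arm changes mix treatment effect with time-of-day drift

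*SAP*

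**What the plan says.** SAP 4.1 defines the vital-sign baseline once: "Baseline Value is defined as the last non-missing value prior to the first IP administration for vital signs, BCVA, biomicroscopy and dilated ophthalmoscopy". The parenthesis that follows names Day 1 Pre-T0 "for vital signs, BCVA and biomicroscopy; Screening for dilated ophthalmoscopy". Two other measures are treated differently: "For IOP and conjunctival hyperemia grading, time-matched baseline values are defined at" Day 1 Pre-T0 for the pre-dose reading and at the same hour on Day 0 for +2, +4, +8 and +12 h.

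The change definitions follow the same split. The general rule, which covers vital signs, is "Change from Baseline is defined as the difference in value of the assessment between the considered visit and the baseline value". The hour-specific rule is restricted: "In the case of IOP and conjunctival hyperemia grading, change from Baseline is the difference in value of the assessment between the considered visit at". That sentence goes on to pair each hour with its own baseline.

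SAP 4.12.2 then plans: "Heart rate and blood pressure (systolic and diastolic), and change from baseline, will be summarized by treatment group, visit and timepoint". SAP 2.6 lists as a safety endpoint "The observed blood pressure and pulse, and change from Baseline at each visit".

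The Time and Events Schedule (protocol Table 1, SAP Appendix 1) places heart rate and blood pressure on Day 0, Day 1 and Day 28 at Pre-T0, +1, +2, +4, +8 and +12 h, and on Day 14 at Pre-T0 only. The +12 h reading is optional for new subjects under Protocol V3.0. Protocol 5.1.2 repeats the instruction for Day 0: "Heart rate/blood pressure at all required timepoints". Day 0 falls 1 to 4 days before the first dose.

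**The concern.** Heart rate and blood pressure can vary over the day without any drug. A change from 8 am to noon or 4 pm contains that variation. The protocol collects what is needed to remove it, an undosed curve at the same nominal hours. That curve includes a +1 h slot at which neither IOP nor hyperemia is measured. Yet no planned vital-sign change score uses it as baseline.

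The secondary objective (protocol section 2, SAP 2.2) is the systemic safety of the H-1337 regimens themselves and, unlike the primary objective, is not framed as a comparison with timolol. SAP 4.12.2 plans only summaries by arm. No arm receives vehicle alone, and timolol, a beta-blocker, may itself move heart rate and blood pressure, so H-1337 minus timolol does not isolate the H-1337 effect. The within-arm change is thus what a reader would turn to. At the post-dose hours it could hide or imitate a modest effect.

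**Working it through.** The plan states no expected change, drift or power for vital signs, so there is no figure of its own to reproduce. The sample size (45 evaluable per group) concerns IOP and has no bearing here.

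**Step 1. Which readings are affected** (from the schedule)

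| Visit | Required on-treatment readings | Compared with another clock time |
|---|---|---|
| Day 1 | +1, +2, +4, +8 h (4) | 4 |
| Day 14 | Pre-T0 (1) | 0 |
| Day 28 | Pre-T0, +1, +2, +4, +8 h (5) | 4 |
| Total | 10 | 8 |

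With the optional +12 h reading on Days 1 and 28, the count is 10 of 12.

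**Step 2. What the change contains.** Let m be a subject's level at 8 am, d(k) the drift from 8 am to hour k, and e(k) the treatment effect at hour k. Take the daily pattern to be the same on Day 0 and on treatment days. In expectation:

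- SAP rule: [m + d(k) + e(k)] − m = e(k) + d(k).
- Day 0 matched: [m + d(k) + e(k)] − [m + d(k)] = e(k).
- H-1337 minus timolol, either rule: e_H(k) − e_T(k), because d(k) cancels.
- Pre-T0 readings: d = 0, so they are already matched.

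**Step 3. Numbers.** All sizes here are assumptions: drift 0, 2, 5 or 8 bpm, H-1337 effect 0, timolol effect −4 bpm. A simulation (50 per arm, 4,000 runs, between-subject SD 8 bpm, within-subject SD 6 bpm) agrees with the formulas. Mean change in bpm, rounded:

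| Drift | H-1337, SAP rule | H-1337, matched | Timolol, SAP rule | Timolol, matched | Difference, either rule |
|---|---|---|---|---|---|
| 0 | 0 | 0 | −4 | −4 | 4 |
| 2 | 2 | 0 | −2 | −4 | 4 |
| 5 | 5 | 0 | +1 | −4 | 4 |
| 8 | 8 | 0 | +4 | −4 | 4 |

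In the row with drift 5, timolol shows −4 + 5 = +1: a real fall is tabulated as a small rise. A downward drift would act in the opposite direction.

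**Step 4. The price of matching.** Let v be the variance of a single reading within a day and w the variance of an independent day-to-day shift. The change on Day 1 has variance 2v from Day 1 Pre-T0 and 2v + 2w from Day 0. The change on Day 28 has variance 2v + 2w under either rule, because both baselines come from another day. The extra between-day variation therefore falls on the Day 1 readings. The simulation used one within-subject SD for every reading, so it does not size w.

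**The case against.** Four objections deserve an answer.

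**The rule is a legitimate choice.** Protocol 8.2 takes the last pre-dose reading as baseline, and the SAP follows it for vital signs. For the acute response on Day 1, a same-day pre-dose value avoids between-day variation. This stands, and it is why the present change should be kept. It does not explain why hyperemia, also a descriptively summarized safety measure, is matched by hour and vital signs are not.

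**A reader might infer that the Day 0 curve goes unused.** The documents do not support that. SAP 4.12.2 summarizes observed values by visit and timepoint, and SAP 3.2 lists Day 0 as a visit, so the Day 0 means may well be printed. With complete data, the matched mean change would then be one subtraction. The paired SD and range would still be missing. Table layouts are in a separate document.

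**A reader might infer that drift is reported as a drug effect.** No section does so. The output is labelled change from baseline, and no test, threshold or decision rule is attached to it. The protocol synopsis names only adverse events as safety endpoints; the vital-sign endpoint appears in SAP 2.6.

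**A reader might infer a bias of known size, or a bias between arms.** Neither follows. The documents give no drift, and zero is possible. Drift common to the arms cancels between H-1337 and timolol and among the three H-1337 regimens, which are tabulated side by side.

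**Conclusion.** The point holds for the within-arm change at +1, +2, +4, +8 and the optional +12 h on Day 1 and Day 28. That change is treatment effect plus whatever time-of-day drift exists, one for one. Its size cannot be derived from the documents: 0 to 8 bpm of assumed drift gives 0 to 8 bpm of shift. The conclusion that Day 0 matching removes the drift rests on the daily pattern being similar on Day 0 and on treatment days, with hours matched nominally (the schedule allows ±30 min).

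Between-arm differences, the Pre-T0 changes on Days 14 and 28, and all efficacy conclusions are untouched. The point matters because the systemic safety of H-1337 is an objective in its own right and Day 0 is the only undosed reference at the same hours. It is a cheap improvement to a descriptive safety table, not an error in the plan.

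**What to change.** - **SAP 4.1, baseline:** add vital signs to the time-matched rule, with Day 1 Pre-T0 for Pre-T0 readings and Day 0 at the same hour for +1, +2, +4, +8 and +12 h. The +1 h entry is new, since the present rule has none.
- **SAP 4.1, change:** extend the hour-specific definition to vital signs; otherwise the new baseline has no effect.
- **SAP 4.12.2:** report the time-matched change, and keep the change from Day 1 Pre-T0 beside it.
- **SAP section 5:** record the departure from the baseline definition in protocol 8.2.

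No new data are needed, and SAP section 1 allows amendment before database lock. The cost is extra table columns, some between-day variation in the matched change, and incomplete pairs at +12 h. The number of pairs should be shown at each hour.

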Administration: Study Design:	The trial will evaluate the safety and efficacy of 3 dose regimens of H-1337 (0.6% b.i.d., 1.0% b.i.d. and 1.0% q.a.m., and timolol maleate (0.5%, b.i.d.) OU for 28 days. Efficacy assessments will be made based upon the study eye. The study eye is the eye that meets all entry criteria including the intraocular pressure (IOP) inclusion criteria. If both eyes qualify the study eye is the eye with the higher 8 am IOP on Baseline (Day 1). If both eyes have the same 8 am IOP on Baseline (Day 1), the study eye is the right eye.
Primary Efficacy Measure:	Change from baseline in IOP in 3 dose regimens of H-1337 compared to timolol 0.5%., b.i.d. at 28 days in subjects with POAG or ocular hypertension.

Secondary Efficacy Measure:	 Mean IOP in 3 dose regimens of H-1337 compared to timolol 0.5%., b.i.d. at 28 days in subjects with POAG or ocular hypertension. Mean diurnal IOP in 3 dose regimens of H-1337 compared to timolol 0.5%., b.i.d. at 28 days in subjects with POAG or ocular hypertension. Proportion of subjects with IOP ≤ 18 mmHg at each time point at each visit, and with the mean diurnal IOP ≤ 18 mmHg for each visit.
Safety Endpoints:	Ocular and systemic Adverse Events (AE)
Study Assessments:	The following assessments and procedures will be performed: • Medical and ocular history • Prior and current concomitant medications and procedures • Adverse events • Heart rate and blood pressure • Best-corrected visual acuity (ETDRS) OU • Biomicroscopy OU • Conjunctival Hyperemia Grading OU • Intraocular pressure (Goldmann tonometry) OU • Gonioscopy OU • Pachymetry OU • Visual field testing (automated, threshold) OU • Ophthalmoscopy (dilated) OU
Statistical Considerations:	This trial has \geq 90% power to detect a clinically significant difference of 2.0 mm Hg, assuming SD of 3.0 mm Hg (ALY337-201), and α =0.05 (1-sided). A hierarchical analysis will be performed starting with 1.0% H-1337 b.i.d. Thus, no adjustment for multiplicity will be performed.
Pharmacokinetic Endpoints	None

Inclusion Criteria:

To be eligible for trial participation subjects must meet all the following criteria:

- 1. 18 years of age or older.
- 2. Diagnosis of bilateral primary open angle glaucoma or ocular hypertension.
- 3. One qualifying IOP criteria after washout:
 - Baseline (Day 1) at T_0 ($T_0 = 8$ am ± 30 min [IOP time]) IOP ≥ 23 mmHg in the study eye.
- 4. IOP criteria after washout ≤ 32 mmHg OU at all qualifying time points/visits.

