4.1 Inclusion Criteria

- 1. 18 years of age or older.
- 2. Diagnosis of bilateral primary open angle glaucoma or ocular hypertension.
- 3. One qualifying IOP criteria after washout:
 - Baseline (Day 1) at T_0 ($T_0 = 8$ am ± 30 min [IOP time]) IOP ≥ 23 mmHg in the study eye.
- 4. IOP criteria after washout \leq 32 mmHg OU at all qualifying time points/visits.
- 5. Best-corrected visual acuity (BCVA) in both eyes of 20/200 or better on Snellen, equivalent to + 1.0 log Mar at Visit 1 Screening.
- 6. Able and willing to sign informed consent, follow study instructions and complete all study visits.
- 7. As applicable, must be willing to discontinue the use of all ocular hypotensive medication(s) in both eyes prior to receiving the study medication and for the entire course of the study.
- 8. Able to self-administer or have a caretaker administer investigational product eye drops.

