4.11.1 Primary Efficacy Analyses

Change from Baseline in IOP (mmHg) at Day 28 and Day 1 (on-treatment time points) in the study eye is the primary efficacy endpoint. It will be summarized by timepoint and treatment group in the ITT population primarily and in the PP population secondarily. The endpoints will be analysed using an analysis of covariance (ANCOVA) model including baseline value and treatment groups as independent variables. The least square (LS) means, standard error (SE) and 2-sided 95% CI will be reported for each treatment group at each post-randomization visit.

In addition, the differences between treatments (H-1337 vs Timolol) will be calculated for each H-1337 treatment group. A time-matched longitudinal model adjusting for baseline and including a random effect for subject will be used to calculate the LS mean, SE, and 2-sided 95% CI for the between-treatments differences. The model will also be tested for treatment by visit and treatment by time points interactions. If no interactions are detected, the main effect model will be used. The variance-covariance matrix-structure used in the model will be the unstructured (TYPE=UN). If convergence is not achieved, a compound-symmetry structure will be used (TYPE=CS).

The testing procedure for non-inferiority will be performed as described in Section 4.3.

Missing values will not be imputed.

All summaries generated for IOP will be using the mean/median value recorded in the case report form.

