4.11.2 Secondary Efficacy Analyses

The secondary efficacy endpoints are all related to IOP in the study eye.

Change from Baseline in IOP at Day 7 and Day 14 in the study eye will be summarised by visit, timepoint and treatment group. The endpoints will be analyzed using an ANCOVA model including baseline value and treatment groups as independent variables. The LS means, SE and 2-sided 95% CI will be reported for each treatment group at each post-randomization visit.

In addition, the differences between treatments (H-1337 vs Timolol) will be calculated and summarised by visit, timepoint and treatment group (for each of the H-1337 groups). The ANCOVA model will be used to calculate the LS mean, SE, and, 2-sided 95% CI for the between-treatments differences.

Similar analyses will be performed for the following endpoints:

- IOP.
- percentage change from Baseline in IOP,
- mean diurnal IOP (12-hour diurnal),
- change from Baseline in mean diurnal IOP (12-hour diurnal),
- percentage change from Baseline in mean diurnal IOP (12-hour diurnal),
- mean diurnal IOP (8-hour diurnal),
- change from Baseline in mean diurnal IOP (8-hour diurnal),
- percentage change from Baseline in mean diurnal IOP (8-hour diurnal).

Where multiple IOP assessments are made on the same day, mean diurnal IOP (12-hour diurnal) is defined as the average of all multiple assessments (Pre T_0 is excluded from the calculation). Mean diurnal IOP (8-hour diurnal) is defined as the average of all assessments up to 04:00pm (Pre T_0 is excluded from the calculation). The visit at which a subject is missing more than (>) 2 assessments for the calculation of mean diurnal IOP will be excluded from the analysis in the PP population.

The number and percentage of subjects with IOP ≤18 mmHg will be summarized by visit, timepoint and treatment group. The 2-sided 95% CI will be calculated using the Clopper-Pearson method. In addition, the difference in proportions between treatments (H-1337 vs Timolol) will be calculated and summarised by visit, timepoint and treatment group (for each of the H-1337 groups). The 2-sided 95% CI for the difference in proportions will be computed using the Wald method.

A similar analysis will be performed for the following 2 endpoints:

- number and percentage of subjects with mean diurnal IOP (12-hour diurnal) ≤18 mmHg, and
- number and percentage of subjects with mean diurnal IOP (8-hour diurnal) ≤18 mmHg.

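### The untreated Day 0 Pre-T0 IOP enters no baseline, change score or covariate in the SAP, which gives up a modest amount of precision at no saving

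*SAP*

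**What the plan says.** **Collection.** The visit list for Day 0 (Protocol 5.1.2) asks for "Goldmann tonometry at all required timepoints". The schedule in the protocol and in SAP Appendix 1 includes Pre-T0 among the Visit 2 time points. Visit 2 falls 1 to 4 days before Day 1, after washout and before any investigational product.

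**Baselines.** SAP 4.1: "For IOP and conjunctival hyperemia grading, time-matched baseline values are defined at" Pre-T0 on Day 1, and at +2, +4, +8 and +12 h on Day 0. The same section adds: "For mean diurnal IOP, baseline is defined at Day 0". However, SAP 4.11.2 leaves Pre-T0 out of both the 8-hour and the 12-hour diurnal mean, so the Day 0 Pre-T0 value does not enter there either.

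**Model.** SAP 4.11.1 uses an ANCOVA "model including baseline value and treatment groups as independent variables" for the arm means. The between-arm intervals come from a time-matched longitudinal model adjusted for baseline with a random subject effect. Neither has a second baseline term.

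**Other roles of the Day 1 value.** Protocol 4.1 requires "IOP ≥ 23 mmHg in the study eye" at 8 am on Day 1. The same reading decides the study eye when both eyes qualify, and it is the Pre-T0 baseline.

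**The concern.** Each subject is scheduled to have two untreated 8 am IOPs a few days apart. Both predict the Day 28 Pre-T0 value, and the plan adjusts for one of them. The one it keeps is truncated by the entry rule, which narrows its range and weakens it as a sole predictor. The later time points adjust for the Day 0 value at the same clock time and use neither Pre-T0 reading.

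Precision matters here because the first hierarchical step requires the upper 95% limit to lie below 1.5 mmHg at every listed time point (9 in SAP 4.3, 7 in Protocol 8.4). One interval that is too wide ends formal testing. A covariate that has already been measured narrows intervals without new data, but it is credible only if named before unmasking.

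**Working it through.** **Inputs from the documents.** 45 evaluable per arm; SD 3.0 mmHg; planning margin 2 mmHg at one-sided 0.05 (SAP 3.3); analysis margin 1.5 mmHg with a two-sided 95% CI, i.e. one-sided 0.025 (SAP 4.3).

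**Assumptions.** True difference zero; SD 3.0 is the residual SD under the planned model; between-visit correlations as listed below.

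**1. The plan's own figure.** SE = 3.0 × √(2/45) = 0.632. Noncentrality = 2/0.632 = 3.16. With 88 df and one-sided 0.05, power is 93.2%, so the stated minimum of 90% holds. Also 45/0.90 = 50.

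**2. At the analysis margin.** Noncentrality = 1.5/0.632 = 2.37. At one-sided 0.025 the power at one time point is 65.0%. The CI half-width is 1.987 × 0.632 = 1.26 mmHg.

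**3. Second baseline, no selection.** With equal correlation r between visits, residual variance is proportional to 1 − r² with one baseline and to 1 − 2r²/(1 + r) with the mean of two.

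| r | one baseline | two baselines | ratio | power at Day 28 Pre-T0 |
|---|---|---|---|---|
| 0.3 | 0.910 | 0.862 | 0.947 | 67.4% |
| 0.5 | 0.750 | 0.667 | 0.889 | 70.1% |
| 0.8 | 0.360 | 0.289 | 0.802 | 74.5% |

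At r = 0.5 the gain equals 45/0.889 = 50.6 subjects per arm at that time point.

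**4. Second baseline, with entry selection.** Simulation: rounded Day 1 IOP 23–32 mmHg, Day 0 at most 32, SD 3, population mean 22–26, Day 0–Day 1 correlation 0.5–0.8, correlation of each baseline with Day 28 0.4–0.6. The SE falls by 1.0% to 7.3%. In variance terms, 1 − 0.990² = 2.0% and 1 − 0.927² = 14.1%. Power at that time point becomes 65.9% to 71.6%, and the half-width 1.24 to 1.17 mmHg. Entering both readings separately gave the same gain as entering their mean.

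**5. Bias check.** Simulation with no drug effect (mean 24, SD 3, r = 0.6, Day 1 selection): mean change from the Day 1 baseline is −0.60 mmHg in both arms, and the between-arm difference is 0.00. Change from Day 0 is also 0.00.

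**6. All-time-points criterion.** Correlated normal estimates, correlation 0.4 to 0.8 between time points, only Day 28 Pre-T0 improved:
- 7 time points: from about 20% (correlation 0.4) or 41% (0.8).
- 9 time points: from about 16% or 38%.
- With a 2–14% variance cut, each rises by about 0.1 to 0.9 percentage point.

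**7. Later time points.** Simulation with between-subject SD 2–3, day-to-day SD 1.5–2.5, response SD 1.5–2 and a subject-by-time SD of 1 mmHg, all assumed. Adding the mean of the two Pre-T0 readings to the +2 h comparison cuts residual variance by about 4–10%, and single-point power goes from 65% to about 67–70%. If every time point gained 4–10%, the model in step 6 gives about 22–25% (from 20%) and 43–46% (from 41%) for 7 time points, and 18–21% (from 16%) and 40–44% (from 38%) for 9.

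**The case against.** The plan is coherent as it stands. One prespecified, pre-dose, time-matched baseline is a normal choice. For Pre-T0 it agrees with Protocol 6.1 (Baseline is Day 1) and with the last-value-before-dosing rule in Protocol 8.2. That is right: this is an improvement, not an error.

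The single-point power gain flatters the change, because success needs every time point. That also stands; step 6 shows how little moves if only Pre-T0 improves.

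The calculations treat one time point at a time, while the intervals come from a longitudinal model that drops to main effects when no interaction is detected. In that branch the per-time-point figures do not carry over directly. SD 3.0 is also not identified as raw, change or residual. Both limit the exactness of the figures, not their direction.

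A second covariate has costs: extra slopes in a model that already has a convergence fallback, and, since missing data are not imputed, the loss of any subject without a Day 0 Pre-T0 value. The fix must deal with this.

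Two stronger readings are tempting:
- **That using the entry reading as baseline biases the comparison with timolol.** It does not. Selection precedes randomisation and acts alike on all arms (step 5). It can only make within-arm Pre-T0 falls look larger.
- **That the value is discarded and the Pre-T0 baseline is a single measurement.** The Day 0 value may appear in summaries of observed IOP by visit, or in the entry check "IOP criteria after washout ≤ 32 mmHg OU at all qualifying time points/visits" (protocol synopsis), where the qualifying visits are not listed. Each IOP is already a mean of two measurements or a median of three.

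**Conclusion.** The point holds as a modest loss of precision. Day 0 Pre-T0 IOP is scheduled for every subject, untreated, and no baseline, change score or covariate in the SAP uses it. The Pre-T0 comparisons (Day 28, and Days 7 and 14 as secondary) rest on the Day 1 value alone.

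The size depends wholly on correlations that the documents do not give. Over the assumed range with entry selection, the variance cut at Day 28 Pre-T0 is anywhere from negligible to worthwhile. At trial level the benefit is small if only that time point gains and a few percentage points at most if all do. Neither repairs the low power at the 1.5 mmHg margin, which is a separate matter.

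**What to change.** In SAP 4.11.1, and in 4.11.2 for Days 7 and 14, keep the change-from-baseline definition and the time-matched baseline covariate. Then add:

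- for Pre-T0 comparisons, Day 0 Pre-T0 IOP as a second covariate;
- for post-dose comparisons, including +12 h where analysed, the mean of the Day 0 and Day 1 Pre-T0 IOPs;
- a rule that, if Day 0 Pre-T0 is missing, the available Day 1 Pre-T0 value is used, so that no randomised subject is dropped. Word this as a baseline-covariate rule, since SAP 4.2 otherwise excludes imputation.

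Endpoint, margin and testing order stay as they are. The cost is at least two extra slopes (more if they vary by time point) and a short SAP amendment before unmasking, which SAP section 1 allows up to database lock. No new data are needed.
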